Crude, as well as age and sex-specific incidence rates of cardiac, thromboembolic (deep vein thrombosis and pulmonary embolism) events, and cardiovascular death during use of SR will be estimated in strata of persons with 0, 1, 2, or more contra-indications amongst persons initiating SR prior and after June 2013. Estimates will be further stratified by age and gender.

The risk of cardiac, thromboembolic events and cardiovascular death will be compared between current use of SR and past use of SR/BP as well as between current use of SR and current use of BP, in persons without contra-indications at start of osteoporosis therapy.

Each case will be matched by age, index date, gender, and country/data source to 10 controls.

Nested case-control analyses will be done using conditional logistic regression.

Sensitivity analyses excluding participating countries where legal restrictions are in place for the prescription of SR in primary care (i.e. Spain) will be reported.

Milestone	Planned date
Protocol submission to EMA	by 30 June 2014
Protocol approval by EMA	March 2015 *
Contract signature for study roll-out phase	April 2015*
Registration in the EU PAS register	April 2015*
Start of data collection	April 2015*
Statistical Analysis Plan	May 2015
End of data collection	End of June 2015
PSUR Update 1	October 2015
Start of data collection (second wave)	April 2016
End of data collection (second wave)	End of June 2016
PSUR Update 2	October 2016
Start of data collection (third wave)	April 2017
End of data collection (third wave)	End of June 2017
PSUR Update 3	October 2017
Final report of study results	End of November 2017

\*Delay will impact the subsequent dates.

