#### 9.2.6.2. Safety study

Patients will be followed from the date of incident prescription of strontium ranelate or oral bisphosphonate (after one year of non-use) which follows the latest of the following dates:

- Start of study period.
- One year of valid data in database.

Until the earliest date of:

- The end of enrolment in the database (due to moving out or death).
- Date of last data capturing in the database.

The safety study will be performed in two periods (up till May 2013 and from June 2013 onwards) based on the date of cohort entry.

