#### Exposure categorization for safety studies

For the incidence rate calculations the period of drug use will be divided in mutual exclusive periods of a month to be able to investigate the rate of cardiac events during current, recent or past use. The period 0-180 days after cessation of study drugs use will be classified as recent use and the period 181 days or more will be classified as past use. If patients switch from SR to BP or vice versa, they will contribute to the respective exposure category.

For the case control study we follow the same categorization. A patient will be classified as current user if the last prescription is ongoing or stopped less than 30 days ago before the index date. Patients will be classified as recent users if last prescription stopped between 30 and 180 days before the index date. Patients are past users if the last prescription for a study drug stopped more than 180 days before index date.

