### 9.5.1. RMM effectiveness study

[figure not shown]
Based on published studies, the combined prevalence of MI, CVD and PAD before the DHPC published in May 2013 is assumed to be of 19.2% in female and 29.5% in male new users of SR (Abrahamsen, 2014).

A total of **320** male users of SR will suffice to estimate with a 95% confidence and an absolute precision of  $\pm 0.05$ , an unchanged prevalence of MI/CVD/PAD of 29.5%. Similarly, **239** female SR users would suffice to estimate with a 95% confidence and an absolute precision of  $\pm 0.05$ , an unchanged prevalence of MI/CVD/PAD of 19.2%.

Regarding the prevalence of new indication/restrictions of use (severe osteoporosis, and second line therapy), recent data suggest that the prevalence of these would range from 13.0% (Svanstrom, 2014) to 53.1% (Abrahamsen, 2014) for previous fragility fracture (severe osteoporosis), and from 40.4% (Svanstrom, 2014) to 47.9% (Abrahamsen, 2014) for the use of SR as a second line anti-osteoporosis treatment. Given this, 383 users of SR would suffice to estimate (with 95% confidence and 5% precision) an unchanged prevalence of 53.1% (most conservative scenario) for both indications. Lower numbers would be needed if this prevalence either increases or decreases (See Figure (9.5.1) 1).

A number of scenarios with different possible prevalence rates of MI/CVD/PAD, previous osteoporotic fracture, and use as a second line anti-osteoporosis therapy amongst SR users in subsequent years in the period before the publication of the DHPC in May 2013 (*reference*) and after the publication of the second DHPC from April 2014 onwards (*assessment* period) are presented in Figure (9.5.1) 1.

**Figure (9.5.1) 1 - Number of SR users required to estimate the prevalence of contraindications or new indication/restrictions with a 5% absolute precision**

[figure not shown]
For the interrupted time series analyses (see details below), sample size calculations are related to the estimation of the number of observations or time points at which data will be collected. According to the quality criteria of Ramsey et al, at least 10 pre- and 10 post-intervention data points would be needed to reach at least 80% power to detect a change (if the autocorrelation is  $>0.4$ ) (Ramsay, 2003). Our outcomes will be estimated at monthly intervals to ensure that  $>10$  data points are available for both the pre-defined *reference* and *assessment* analysis periods.

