### **9.7.3.2. Absolute rates of safety endpoints**

The crude and age and sex specific incidence rates of each of the safety endpoints events will be estimated separately in new SR and oral bisphosphonate users assuming a Poisson distribution. Incidence rates will be stratified by period (up till May/2013 and from June/2013 onwards) and by number of newly defined (contra) indications at cohort entry. Graphs will be created that show the incidence rates of endpoints during use of study drugs and after use of study drugs.

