## Confounding

Due to the observational design chosen, causality in the observed associations will not be established. Instead, associations between drug use and risks will be assessed. As confounding by indication (with SR patients most likely to suffer more severe osteoporosis) will likely produce differences between SR and bisphosphonate users, especially after the different DHPCs, we will use several methods to deal with between-person confounding:

1. Restriction: comparative studies will be conducted only in persons without contra-indications to restrict the population to those that would be prescribed SR according to the new label.
2. Matching: for the comparative studies we will match cases to controls on age, sex, date, country.
3. Adjustments: we will adjust for all co-variables that are associated with a 10% change in the primary risk estimate.

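### The safety-study passages disagree on the date that fixes period and contraindication status for patients who switch between an oral bisphosphonate and strontium ranelate

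*Protocol*

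**What the plan says.** Four places in the protocol describe one cohort entry per patient with exposure changing over time:

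- Section 9.2.6.2 starts follow-up at an incident prescription of SR or an oral BP and ends it only at end of enrolment or last data capture. The analysis is in "two periods (up till May 2013 and from June 2013 onwards) based on the date of cohort entry".
- Section 9.3.3 (exposure categorization): "If patients switch from SR to BP or vice versa, they will contribute to the respective exposure category".
- The abstract (data analysis, safety) makes the SR–BP comparison "in persons without contra-indications at start of osteoporosis therapy".
- Section 9.7.3.2 stratifies rates "by number of newly defined (contra) indications at cohort entry".

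Four other places point to the SR start:

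- The same part of the abstract reports rates "amongst persons initiating SR prior and after June 2013".
- Section 9.2.2 explains the June 2013 cut as the point from which patients with a new contraindication should no longer receive SR.
- Section 9.3.2 looks back for every contraindication from the start of SR therapy.
- Section 9.9 (Confounding) relies on the exclusions to "restrict the population to those that would be prescribed SR according to the new label".

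Section 9.2.5.3 dates its hypertension criterion from initiation of either drug, so it fits both readings. No passage says whether a BP user who later starts SR makes a second cohort entry.

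**The concern.** Safety objective 2 compares SR with oral BP in patients without contraindications, before and from June 2013, and Section 9.7.3.3 stratifies every relative-risk analysis by period. The date that assigns a patient to a period and clears her of contraindications therefore shapes a primary comparison.

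With a single entry date, three things follow for a patient who enters on a BP before June 2013 and starts SR afterwards. Her SR exposure is filed in the earlier period. The later period, which has few SR starters, loses that exposure. Any contraindication that arose between the two drugs is ignored, unless it is itself the endpoint being analysed.

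**Working it through.** **1. One patient under each reading.** She starts alendronate in 2009, has a stroke in March 2014 and starts SR in September 2014. The stroke lies within the one-year look-back of 9.3.2.

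- *Single entry (9.2.6.2 with 9.3.3):* entry 2009; period up to May 2013; no contraindication at entry. Her SR time counts as current SR use in the earlier stratum of the comparison. Stroke is not among the three endpoints in 9.3.1, so nothing else removes her.
- *Dating from SR start (abstract rates, 9.3.2):* period from June 2013; stroke counted; excluded from the comparison, and placed among patients with a contraindication for the rates.

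**2. The plan's own counts (9.5.2).** Excluded share: 0.10 × 0.295 + 0.90 × 0.192 = 0.2023. Eligible SR users: 31,500 × (1 − 0.2023) = 25,127.55, i.e. the stated 25,128. BP users: 5 × 25,128 = 125,640. MI cases: 150,000 × 0.0019 × 2 = 570. All three reproduce.

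**3. Upper bound on misfiled SR starters.** Section 9.5.2 expects 500 to 1,000 SR starters a year in 2013–2015, so 1,500 to 3,000. Section 9.5.1 gives 40.4% to 47.9% "for the use of SR as a second line anti-osteoporosis treatment". Assume that all of these second-line users entered on an oral BP before June 2013:

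- 1,500 × 0.404 = 606; 1,500 × 0.479 = 718.5
- 3,000 × 0.404 = 1,212; 3,000 × 0.479 = 1,437

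The range is 606 to 1,437. Against the at least 30,000 SR starters expected for 2004–2012, that is 606/30,000 = 2.0% to 1,437/30,000 = 4.8%. By headcount, contamination of the earlier stratum is modest and the effect falls mainly on the later one.

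**4. The later stratum.** As assumptions, carry over the 20.23% exclusion, five BP users per SR user, an MI rate of 0.0019 per year and two years of follow-up. Total cases are N × 0.7977 × 6 × 0.0038, which gives 27.3 for N = 1,500 and 54.6 for N = 3,000. Take exposure in controls p0 = 1/6, exposure in cases p1 = 1.5p0/(1 + 0.5p0) = 0.231, ten controls per case and two-sided alpha 0.05. An unmatched two-proportion comparison then has power of about 16% and 24% for an odds ratio of 1.5.

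If 40.4–47.9% of the SR users move out and the BP users stay, p0 falls to 0.107–0.094. Cases fall to about 25 (N = 1,500) or 50–51 (N = 3,000), and power to about 13% and 18–19%.

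**The case against.** The best counter-argument is that the protocol can be read as entering switchers at SR start. Sections 9.2.3 and 9.2.4 define new use drug by drug and do not bar earlier BP use. Section 9.5.2 counts incident SR users by calendar year of SR start and deducts only contraindications, nothing for prior BP use. Section 9.3.4 records other osteoporosis drugs in the year before entry. This stands: the text is an unresolved conflict, and a reader who infers an unambiguous rule fixing everything at the first osteoporosis drug goes beyond it. But no passage grants a second entry, and 9.2.6.2, 9.3.3 and 9.7.3.2 together read the other way.

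A reader might also infer that the later comparison loses the second-line SR users it exists to assess. The documents do not support that. Switchers would be reallocated, not dropped. Second-line use is a question for the risk-minimization study (9.3.2, 9.7.2.2), not safety objective 2. Patients whose earlier drug was not an oral BP, whose BP start was not observed as incident, or who began a BP from June 2013 onwards stay in the later period.

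Nor does it follow that a fracture prompting the switch escapes adjustment. Section 9.3.4 measures confounders at index date as well, and 9.7.3.3 allows index-date factors that cannot be intermediates. Controls are also matched on index date, so calendar time does not confound the odds ratio within a stratum. An MI while on a BP is already the endpoint in the MI analysis.

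Finally, time-varying exposure within one cohort is a legitimate design. Compulsory censoring at the switch would remove past-use time that the first contrast in 9.7.3.3 needs.

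**Conclusion.** The passages conflict on which date fixes period and contraindication status for switchers, and they need to be reconciled before data extraction. If 9.2.6.2 and 9.3.3 are followed as they read, the period strata and the restriction described in 9.9 do not do what 9.2.2 and 9.9 say they do for these patients.

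The size cannot be derived from the documents. The 606 to 1,437 is an upper bound at the quoted second-line shares for the starters expected in 2013–2015. It includes January–May 2013 starters, contraindicated patients whom the comparison excludes, and users whose earlier drug was not an oral BP. Two unknowns lie outside the bound: the second-line share after the restriction is not given and could be higher, and SR starters after 2015 are not counted. A firm percentage of misfiled starters would rest on shares that the documents do not contain.

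The later stratum is weak for MI on either reading, at roughly 16–24% power on the carried-over assumptions. Reallocation makes it weaker but is not the cause of the weakness.

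**What to change.** State one switcher rule in 9.2.6.2, 9.3.3, 9.7.3.2 and the abstract. Assign period, and assess the 9.2.5.3 exclusions and baseline covariates, at the start date of the study drug being analysed: SR start for SR exposure, BP start for BP exposure. Recent and past use would follow the drug last used. Adjust for prior use of the other study drug.

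Align the wording of 9.2.5.3 and 9.3.2 to the same date, so that contraindications are also defined for BP starters. In the abstract, replace the reference to the start of osteoporosis therapy. Period is not among the matching factors, so also say that controls are drawn from the same period as their case.

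Make censoring of the first episode at the switch a sensitivity analysis, not a requirement.

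The cost is wording and some extraction-script work. Some patients contribute two entries, and switchers who acquired a contraindication leave the comparison, so there are slightly fewer cases.

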### 9.3. Variables

#### 9.3.1. Safety endpoints

**Ascertainment of cases:** cases will be all persons with a first occurrence after cohort entry of:

- Acute myocardial infarction.
- Thromboembolic events (deep venous thrombosis and pulmonary embolism).
- Cardiovascular death.

Cases will be identified from the medical records (see codes in Appendix 14.3).

Acute myocardial infarction has been recently validated in all of the participating data sources (Coloma, 2013; Ramos, 2012) and will therefore not need further linkage or validation studies.

Thromboembolic events have been validated in the UK CPRD/THIN (Lawrenson, 2000) and Aarhus (Severinsen, 2010), and these previously validated algorithms will be used to identify cases. A random sample of cases of thromboembolic events in each data source will be validated using either free text manual review (IPCI, HSD, and Aarhus) or linkage to hospital admissions data (THIN and SIDIAP). If the estimated positive predictive value in these samples is >75%, no further validation will be performed for thromboembolic events. Otherwise, all the events observed in the safety study (i.e. cases) will be individually validated, and only those found to be valid (either by manual review or related hospital admission from hospital records databases, as proposed above) will be defined as cases.

As for cardiovascular death, HSD, IPCI and SIDIAP will combine ICPC and ICD9/ICD10 codes (for hospital admission/primary care records) respectively with mortality using a time specific window to define cardiovascular death. In THIN, data will be linked to the official mortality registry (office for national statistics) for cause of death. In Aarhus, safety endpoints will be identified in the patient registry (hospital discharge and death registry) and no manual validation in the medical records will be done.

**Control selection:** In the nested case control study, each case will be matched by age (same year of birth), index date, gender, and country/data source to 10 controls selected from the cohort using incidence density sampling.

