### 9.2.5.2. Incidence rates of safety endpoints

None.

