### 9.2.5.3. Comparative safety study

Patients with any of the newly defined contra-indications will be excluded:

1. Established, current or past history of ischemic heart disease (IHD),
2. Peripheral arterial disease (PAD),
3. Cerebrovascular disease (CVD),
4. Uncontrolled hypertension, defined by MAH using an operational definition as follows: a patient will be defined as 'uncontrolled hypertension' if the 3 following conditions apply:
  - a. There is a previous diagnosis of hypertension coded in electronic medical records.
  - b. There is documented use of any anti-hypertensive therapy (either at that time or in the previous year before SR/BP initiation).
  - c. There are at least two readings of Systolic Blood Pressure  $\geq 150$  or Diastolic Blood Pressure  $\geq 95$  mmHg recorded in the 3 months prior to SR/BP initiation.

Also, eligible patients with a diagnosis of Paget's disease of bones will be excluded. And for the outcome VTE we will exclude patients with a previous VTE.

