### 9.4.3. THIN Database

The Health Improvement Network (THIN) is a database of primary care medical records from the UK. General practitioners are trained to complete their medical records using the Vision general practice computer system (InPractice Systems, London, UK). This electronic record serves as the primary medical records for the practice.

Data recorded in THIN include demographics, details from GPs' visits such as medical diagnoses and prescriptions written by the GPs, diagnoses from specialist referrals and hospital admissions, some results of laboratory tests, some lifestyle characteristics and other measurements as taken in the practice. Within the database, diagnoses are recorded using READ codes. Prospective data collection for THIN began in September 2002, with electronic medical records that date back to 1985. In addition, practices may retrospectively enter significant medical events into the electronic medical record. Currently, the database has 2.7 million active patients registered. Recently a validation study was conducted by Lewis *et al* (2007) which concluded that "THIN data that are collected outside of the Clinical Practice Research Datalink (CPRD) appear as valid as the data collected as part of the CPRD".

As the primary aim of the collection of data in the THIN database is patient management, data will reflect only those events that are deemed to be relevant to patient's care. In addition; use of THIN data is not appropriate in studies where individual ethnicity, occupation, employment, and/or socio-economic status are important variables. As for all prescription databases, over-the-counter (OTC) drug use and non-compliance to medication prescriptions might be an issue. As the average follow-up within the THIN database is 5.5 years, the THIN database is not suitable to conduct long-term follow-up studies. Approval needs to be obtained for each study from the THIN governance board.

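### The absolute-rate analysis has no new-episode rule, so a re-recorded earlier MI or VTE can count as an incident event, mainly in strata with a recent event of the same type

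*Protocol*

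**What the plan says.** **Case definition.** Protocol 9.3.1: "cases will be all persons with a first occurrence after cohort entry of" acute MI, thromboembolic events or cardiovascular death. It sets no requirement on earlier events and no minimum gap from one.

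**Exclusions.** For the incidence rates, 9.2.5.2 consists of the single word None. Only 9.2.5.3, which governs the comparative study, removes patients with past ischaemic heart disease, and adds: "for the outcome VTE we will exclude patients with a previous VTE".

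**Strata.** The abstract (section 4, Safety) gives the rates "in strata of persons with 0, 1, 2, or more contra-indications". Section 9.7.3.2 stratifies "by number of newly defined (contra) indications at cohort entry". Section 9.3.2 counts MI (within ischaemic heart disease) and VTE as contra-indications when recorded in the year before SR start.

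**Washout.** The one-year washout in 9.2.2 and 9.2.3 concerns data availability and drug use, not events.

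**Safeguards.** Starred codes in Appendix 14.3.2 describe history and may not identify new events. VTE is validated in a sample per database, and in full only if the positive predictive value (PPV) is not above 75% (9.3.1). MI gets no further validation (9.3.1). Event rates are benchmarked per database (9.6.4).

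**The concern.** The contra-indicated strata hold patients whose qualifying condition can be the same type of event as the endpoint. If the acute code for an MI three months before SR start is entered again at a review one month after it, the printed rule counts an incident MI during SR use. The star rule does not stop this, because the code is an acute one.

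Four of the five sources are medical-record databases (Table (9.4) 1). For one of them, THIN, section 9.4.3 says that "practices may retrospectively enter significant medical events into the electronic medical record".

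At stake is a primary safety objective: the event rates in SR users with and without contra-indications. Such false events would raise the first set more than the second. If re-entry happens mostly soon after the original event, they would also raise the early part of the planned graphs of rates during and after drug use (9.7.3.2).

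**Working it through.** **1. What the rules do when read together.**

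| Question | Absolute rates | Comparative study |
|---|---|---|
| Prior MI in the cohort? | Yes (9.2.5.2) | No (9.2.5.3) |
| Prior VTE in the cohort, for the VTE outcome? | Yes (9.2.5.2) | No (9.2.5.3) |
| Rule separating a new event from a repeat code? | None stated | Not needed for MI or VTE before entry |

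*First occurrence after cohort entry* could also be read as first ever. Patients with a prior MI could then never become MI cases but would still add person-time, which would pull their rate down. Both readings distort the rate, in opposite directions.

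**2. Gaps in the starred list, as printed in 14.3.2.**
- ICD-9 V12.51 and V12.55 (personal history of venous thrombosis/embolism and of pulmonary embolism) carry no star. The matching READ personal-history terms do.
- READ G32.. stands unstarred beside acute subendocardial infarction, while G32..00 is starred as old or healed MI.
- ICD-9 410.62 is starred, but 410.72 is not.

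**3. The plan's own event count.** Section 9.5.2 uses 0.19 MI per 100 person-years, 2 years of follow-up and over 150,000 persons: 150,000 × 2 × 0.0019 = 570, as stated. With the unrounded sizes, (25,128 + 125,640) × 2 × 0.0019 = 572.9. This checks the base rate; the point itself rests on the definitions.

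**4. Possible size.** Apparent rate per 100 person-years = I + 100 × s × r / T, where
- I = true rate in the stratum;
- s = share of the stratum with an MI in the prior year (assumed 5% to 25%);
- r = share of those whose acute code is entered again after SR start (assumed 1% to 20%);
- T = 2 years (9.5.2).

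The documents give neither s nor r.

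| I | s, r | Apparent rate | Ratio to I |
|---|---|---|---|
| 0.19 (9.5.2) | 5%, 1% | 0.19 + 0.025 = 0.215 | 1.13 |
| 0.19 | 10%, 5% | 0.19 + 0.25 = 0.44 | 2.32 |
| 0.19 | 25%, 20% | 0.19 + 2.5 = 2.69 | 14.2 |
| 1.9 (assumed, ten times higher) | 5%, 1% | 1.9 + 0.025 = 1.925 | 1.01 |
| 1.9 | 10%, 5% | 1.9 + 0.25 = 2.15 | 1.13 |
| 1.9 | 25%, 20% | 1.9 + 2.5 = 4.40 | 2.32 |

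The 0.19 is a general-population rate, so the upper block probably overstates the ratio for patients with contra-indications.

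**5. Comparison with the MI validation.** Section 9.9 reports PPVs of 75% to 100% for MI coding. A stratum PPV of 75% would correspond to a ratio of 1/0.75 = 1.33. The overall PPV does not bound the PPV in a small stratum with prior MI, and the protocol does not say whether those validations separated new from earlier events.

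**The case against.** **This is extraction or SAP detail.** Section 9.6.2 leaves the event algorithm to consensus, code lists will be discussed further before extraction, and 9.7 announces a detailed SAP. A repeat-code interval is often set there. This lowers the urgency. But the protocol itself fixes the case definition and the absence of exclusions, and an algorithm that follows them literally counts repeats.

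**The mechanism is documented for one source only.** This stands. Section 9.4.3 concerns THIN, which supplied 514 of 5,819 incident SR users in 2012 (8.8%), against 4,008 (68.9%) in SIDIAP and 1,209 (20.8%) in HSD. It mentions retrospective entry, not re-entry of an acute code at follow-up visits. Re-recording elsewhere is plausible but not shown.

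**The strata are not cleanly separated.** This also stands. With a one-year look-back, a patient with an older MI or VTE and no other contra-indication sits in the zero stratum. Section 9.7.3.2 speaks of newly defined contra-indications, and 9.2.5.3 keeps VTE apart from that list, although the abstract and 9.3.2 include it. If VTE does not count toward the strata, repeated VTE codes could fall in any of them.

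**Safeguards exist.** The stars and the VTE sample check reduce the problem. They do not remove it: stars do not cover repeated acute codes, VTE checking stops once the sample PPV exceeds 75% and is not required by stratum, and benchmarking looks at whole databases.

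**Stronger readings a reader might infer.** One is that objective 1 formally compares rates with and without contra-indications; sections 4 and 8 say estimate, and comparison belongs to objective 2. Another is that the verdict on the risk-minimization measures is biased; that rests on interrupted time series of prevalence (9.7.2.2), which this issue does not touch. A third is that the SR-versus-bisphosphonate odds ratio is biased; 9.2.5.3 excludes prior ischaemic heart disease and, for VTE, prior VTE.

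**Conclusion.** The point holds for the absolute MI and VTE rates of safety objective 1. As written, an acute code re-entered for an event before cohort entry, or an unstarred history code, can be counted as incident. The effect would fall mainly on strata with a recent event of the same type, with some leakage into the zero stratum from older events.

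The documents do not support saying that such events will be counted in exactly the contra-indicated strata, or by how much. The ratios of 1.01 to 2.3 (true rate 1.9 per 100 person-years) and 1.13 to 14.2 (true rate 0.19) rest on assumed values of s and r, and the first range also on an assumed true rate. They show only that the effect could be negligible or large. MI is the more exposed endpoint because no further validation is planned for it. The correction is worth making because it touches a primary objective and is cheap.

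**What to change.** 1. In 9.3.1, for the rate analysis, state that in a patient with an earlier record of the same event a post-entry MI or VTE code counts only if it is linked to a new hospital admission or follows a fixed interval free of that event's codes. Fix the interval before extraction. Table (9.4) 1 lists hospitalizations as available in all five sources.
2. In 9.7.3.2, also report the rates after excluding patients with a prior event of the same type, as 9.2.5.3 already does for VTE in the comparative study.
3. In 14.3.2, reconcile the stars for V12.51 and V12.55, for READ G32.., and for 410.62 against 410.72.
4. State whether VTE counts toward the strata in 9.7.3.2.

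The cost is one rule in the extraction algorithm, one extra table and a code-list check, all on data already planned. The downside is that true early recurrences inside the clean interval and without a recorded admission are missed.
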